Primary Effectiveness:	
 
Device and procedure related serious adverse events at 30 days and 6 months
 
Technical Success, defined as the ability of the Cardio Flow FreedomFlow™ Orbital Atherectomy System to achieve a residual diameter stenosis ≤50% post treatment without adjunctive therapy, as assessed by an Angiographic Core Laboratory.
 
				
Secondary Effectiveness:	• Clinical Success, defined as the ability of the Cardio Flow FreedomFlow TM				

Orbital Atherectomy System to achieve a final residual diameter stenosis ≤50% with adjunctive therapy, determined by independent angiographic core laboratory.

- Procedure Success, defined as:
  - No procedure-related MAE
  - $\circ$   $\leq$  50% residual stenosis at target lesion
  - O No device malfunction causing the procedure to be aborted
- Percent of device run time less than 3 minutes cumulative total
- Maximum balloon inflation pressure of the adjunctive plain balloon angioplasty and/or drug coated balloon angioplasty
- Improvement of ABIs at 30 days and 6 months
- Improvement of Rutherford Classification at 30 days and 6 months
- Improvement of patient reported outcomes (PRO, VascuQoL questionnaire) at 30 days and 6 months
- Clinical driven target lesion revascularization (TLR), target vessel revascularization (TVR) at 30 days and 6 months (to be evaluated by angiographic core laboratory)
- Primary patency, primary assisted patency and secondary patency at 30 days and 6 months. Doppler ultrasound examinations at 30 days and 6 months to confirm patency (to be evaluated by duplex ultrasound core laboratory). The restenosis is defined as peak systolic velocity ratio (PSVR) of 2.5.

#### **Inclusion Criteria:**

Subjects must meet all of the following criteria to be eligible for participation in the study:

#### Inclusion Criteria

- 1. Age  $\geq$  18 years old.
- 2. Subject is a candidate for percutaneous endovascular intervention for peripheral vascular disease in the lower extremity.
- 3. Disease is located in the common femoral, superficial femoral, popliteal, anterior tibial, posterior tibial, or peroneal artery in arteries.
- 4. Objective hemodynamic criteria that subject has a resting ankle-brachial index (ABI) ≤ 0.90, OR subjects with non- compressible arteries (ABI>1.1) must have a toe-brachial index (TBI) of ≤ 0.80.
- 5. Clinical presentation of lifestyle limiting claudication or rest pain as characterized by Rutherford Classification 2, 3, 4, or 5.
- 6. Subject has de novo target lesion(s) or lesion(s) treated by percutaneous transluminal angioplasty (PTA) only greater than 3 months prior with stenosis ≥70% by visual estimation in the common femoral, superficial femoral, popliteal, anterior tibial, posterior tibial, or peroneal artery. Up to three lesions can be treated at the index procedure provided the cumulative total lesion length is ≤ 30 cm AND all lesions are in the same leg.
- 7. Target reference vessel diameter (proximal to and distal to target lesion) is 2 to 5mm by angiographic visual estimation.
- 8. At least one patent vessel run-off to the ankle or foot at baseline.
- 9. The target lesion(s) can be successfully crossed with a commercially available 0.014" atherectomy guidewire without any complications during wiring

## procedure. 10. Subject signs a written Informed Consent form to participate in the study, prior to any study mandated determinations or procedure. Subject must be excluded from participation in this study if any of the following **Exclusion Criteria:** criteria are met: Exclusion Criteria 1. Is female with childbearing potential not taking adequate contraceptives or is currently breastfeeding. Target lesion is within a native graft or synthetic graft. Target lesion is an in-stent restenosis. Chronic total occlusion (CTO) with wire crossed near the advential junction. Subject has significant stenosis or occlusion of inflow tract (upstream disease) not successfully treated during the index procedure and prior to treatment of the target lesion. History of an endovascular procedure or open vascular surgery on the index limb within 30 days prior to the index procedure. Planned endovascular or surgical procedure within 30 days after the index procedure. 8. Signs and symptoms of systemic infection (temperature of $\geq 38.0^{\circ}$ Celsius and/or WBC of $\geq$ 12,000 cells/ $\mu$ L) at the time of assessment; Note: If infection is adequately treated and controlled (temperature $38.0^{\circ}$ C and WBC < 12,000 cells/ $\mu$ L) patient may be enrolled. 9. Unstable coronary artery disease or other comorbid condition(s) that, in the judgment of the physician precludes safe percutaneous intervention. 10. Significant acute or chronic kidney disease with a creatinine level > 2.5 mg/dL and/or requiring dialysis. 11. Evidence or history of intracranial or gastrointestinal bleeding, intracranial aneurysm, myocardial infarction or stoke within 2 months of index procedure. 12. Evidence or history of aneurysmal target vessel. 13. Clinical/angiographic evidence of distal embolization. 14. Known allergy to contrast agents or medications used to perform endovascular intervention that cannot be adequately pre-treated. 15. Subjects in whom anti-platelet, anticoagulant, or thrombolytic therapy is contraindicated. 16. Heparin-induced thrombocytopenia (HIT) not able to use Bivalirudin. 17. Uncorrectable bleeding diathesis, platelet dysfunction, thrombocytopenia with platelet count less than 125,000/mm2, known coagulopathy, or INR > 1.5. 18. Thrombolytic therapy within 2 weeks of the index procedure. 19. Intra-operative (intra-procedure) clinical or angiographic complication (other than non-flow limiting dissections) attributed to the use of a currently marketed device prior to introduction of the Cardio Flow atherectomy driveshaft. 20. Has life expectancy < 12 months. 21. Subject is unwilling or unable to comply with the follow-up study requirements. 22. Is currently participating in an investigational drug or another device study.

	23. Has one or more stents in the treatment vessel.		
	24. Lacking capacity to provide consent.		
Study Duration / Follow- up Period:	Approximately 2 months enrollment period with observation periods at time of procedure, 30 days post procedure and 6 months post procedure. An interim report will be prepared after 30-day follow-up of all subjects. A final report will be prepared following completion of 6-month follow-up of all subjects.  Subjects will be followed per protocol and institutional standard of care for		
	atherectomy treatment of PAD.		
Analysis Population	The primary analysis will be based on the intent-to-treat (ITT) population.		

#### 1 BACKGROUND AND RATIONALE

Atherosclerosis causes symptomatic disease primarily in the coronary arteries, the peripheral arteries of the lower extremities, and the extra-cranial carotid arteries. Of the three, peripheral artery disease (PAD) is probably the most under-diagnosed and least aggressively managed, despite its strong association with cardiovascular disease (CVD) and death. PAD is chronic occlusive artery disease of the lower extremities and a strong surrogate marker for atherosclerosis in the heart, kidneys, and brain. PAD is associated with a 60% incidence of coronary or cerebrovascular disease. About 90% of patients with symptomatic PAD have coronary artery disease (CAD) as well. The disease can have devastating effects on quality of life and survival, with mortality around 30% in 5 years, 50% in 10 years and 75% in 15 years. Overall, CVD causes death in 75% of PAD patients.

Most common among elderly people, diabetics, and smokers, PAD afflicts an estimated 8-12 million people in the United States alone. Its prevalence is likely to increase greatly in the next several decades as the risk factors of diabetes, smoking, hypertension, dyslipidemia and cardiovascular incidence increase.

Classic symptoms of PAD include intermittent claudication (IC), defined as leg muscle pain or weakness that occurs during walking and subsides with rest. The exercise-induced symptoms are distal to the obstruction in the artery that supplies the leg. Rest pain in the toes or foot indicates that arterial blood flow cannot meet the needs of resting metabolism. The resulting critical limb ischemia (CLI) can progress to ulceration or gangrene in the toes, ankle, heel, or leg, often necessitating amputation.

Even asymptomatic PAD patients, those without IC, have poor physical function. Detecting asymptomatic PAD requires measuring and calculating the ankle/brachial index (ABI), obtained by dividing blood pressure measured in the ankle by the blood pressure measured in the upper arm. In a healthy person, the ABI is 0.9 to 1.2. An ABI under 0.9 is 95% sensitive and 99% specific for the diagnosis of PAD. The lower the ABI level, the more serious is the ischemia. An ABI of 0.5 is associated with a 63% five-year survival rate, and ABIs between 0.25 and 0.4 are often associated with rest pain and tissue loss. Patients with normal ABIs and IC are advised to undergo an exercise ABI assessment. Patients with calcified, relatively incompressible arteries from diabetes or renal disease may have false normal ABIs. To diagnose such patients, vascular laboratories can measure a toe/brachial index or do other noninvasive testing. Physicians can also use an exercise ABI measurement to assess IC patients with normal ABI scores. Physicians can also

The overall goals of PAD treatment are to maintain or improve function, reduce or eliminate ischemic symptoms and prevent disease progression. Current treatments include exercise, medical treatment to lower cholesterol and blood pressure, and surgery or percutaneous interventions to restore blood flow in patients with intermittent claudication (IC) or critical limb ischemia (CLI). Invasive treatments include bypass surgery, percutaneous transluminal angioplasty (PTA), percutaneous atherectomy (directional or rotational), endarterectomy, excimer laser combined with PTA and stenting (drug-eluting stents) of the occluded or stenosed vessel. Therapeutic angiogenesis, which uses angiogenic growth factors or bone marrow mononuclear cell therapy to stimulate growth of new blood vessels, and subintimal

angioplasty, in which a new lumen is tunneled between the intima and the media, are under study. 19, 20

Technical challenges involved in treating PAD surgically or percutaneously arise from anatomy, co-existing diseases such as diabetes, restenosis, inflammation and disease progression. Surgery or percutaneous interventions in the aorto-iliac arteries have better results than in the femoropopliteal arteries, and in turn, results in the femoropopliteal arteries tend to be better than those in the smaller lower-leg arteries.

Atherectomy is a minimally invasive endovascular technique for removing atherosclerotic plaque from blood vessels within the body. There are three main types of atherectomy devices: directional, laser, and rotational, which includes a subset known as orbital. The current U.S. Food and Drug Administration (FDA) cleared devices for peripheral atherectomy include the SilverHawkTM, TurboEliteTM, RotoblatorTM, DiamondbackTM, JetStreamTM, PhoenixTM, and PantherisTM. Cardio Flow, Inc. has pioneered advances in orbital atherectomy technology for the intravascular treatment of PAD using the Cardio Flow FreedomFlowTM Orbital Atherectomy System.

The Cardio Flow FreedomFlowTM Orbital Atherectomy System is intended to remove fibrous and calcified stenotic plaque using diamond-coated eccentric spheres attached to a driveshaft in a spiral configuration. The device intended to operate over a commercially available 0.014' atherectomy guidewire to treat vessels from 2mm to 5mm in diameter. No driveshaft lubricant is required for use with the Cardio Flow FreedomFlowTM Orbital Atherectomy System.

One GLP-like porcine studies (2 pigs) were conducted to assess safety and device performance in normal peripheral arteries a range of vessel sizes. Devices were operated according to the Instruction for Use. Animals were survived for three days post-treatment and the treated vessels were harvested and histopathological evaluation performed.

One human cadaver study (3 limbs) was also conducted according to the Instruction for Use. The limb studies were utilized to obtain particulate from the atherectomy procedure for a size distribution analysis and to observe device operation in occluded arteries.

#### 2 DEVICE DESCRIPTION AND USE

# 2.1 Device Description

The FreedomFlowTM Orbital Atherectomy System consists of a Control Module, Tubing Set, and User Handle. It is designed to remove atherosclerotic plaque from peripheral arteries by rotation of diamond-coated spheres mounted eccentrically on a coiled driveshaft. The Control Module is reusable capital equipment. The Tubing Set and User Handle are single-use sterile devices. The User Handle is used to activate rotation and advance the driveshaft on a commercially available 0.014-inch bare-metal atherectomy guidewire. The guidewire and introducer sheath are not included with the system. The Tubing Set and User Handle are the only parts of the system applied to the patient.

[figure not shown]

Figure 2-1: FreedomFlowTM Orbital Atherectomy System

#### 2.1.1 Control Module

The Control Module, Model CM1001, is a portable, reusable component of the system that integrates delivery of saline and pneumatic power to the User Handle. The Control Module touchscreen is the primary interface for operating the peristaltic pump and regulating orbital speed of the User Handle. The pre-programmed Control Module includes a pneumatic pressure hose and hospital-grade electrical plug. The Control Module can be placed on a table or mounted to a standard 5-wheel IV pole.

[figure not shown]

Figure 2-2: Control Module

# 2.1.2 Tubing Set

The Tubing Set is a single-use component that is packaged with the User Handle. The Tubing Set is supplied sterile (via Ethylene Oxide gas). The set delivers saline and pressurized gas from the Control Module to the User Handle. A cable and sensor relay orbital speed back to the Control Module.

Figure 2-3: Tubing Set

#### 2.1.3 User Handle

The User Handle is a single-use component that provides control over rotation and translational movement of the integrated driveshaft. The User Handle is supplied sterile (via Ethylene Oxide gas). A spring-loaded button on the User Handle is depressed to activate the pneumatic driveshaft and released to stop rotation. The turbine carriage of the User Handle has 7 cm of travel and is used to advance and retract the driveshaft's diamond-coated distal tip and eccentrically mounted diamond-coated spheres independently of the catheter tubing. The User Handle guidewire clamp prevents guidewire movement during use. User Handle H4001 will be evaluated in this clinical trial and can be used to treat a range of vessel sizes. Refer to Instructions for Use for guidance on appropriate vessel sizes that can be treated with User Handle H4001.

Figure 2-4: User Handle

#### 2.1.4 Driveshaft Details

The driveshaft is a hollow multi-strand cable that drives the spinning of the diamond-coated spheres. The off-axis eccentric attachment of the spheres onto the driveshaft force the spheres in an outward centrifugal direction during rotation. The diamond-coated distal tip is designed to add stability and may ease transition into a tight stenotic lesion.

[figure not shown]

Figure 2-5: Driveshaft Tip

The Cardio Flow Orbital Atherectomy User Handle and Tubing Set are sterile, disposable devices that are intended for use during a single patient procedure and are used with the Control Module, which is a non-sterile, reusable unit that controls system operation.

#### 2.2 Intended Use

The FreedomFlowTM Orbital Atherectomy System is a minimally invasive, catheter-based system designed for improving luminal diameter in patients with PAD.

## 2.3 Indication For Use

The FreedomFlowTM Orbital Atherectomy System is applied as therapy to remove atherosclerotic plaque within peripheral arterial vessels. The therapy is intended for patients who are acceptable candidates for percutaneous transluminal atherectomy.

#### 3 STUDY PURPOSE AND OBJECTIVE

The primary objective of the study is to evaluate the first-in-human safety and effectiveness of the FreedomFlowTM Orbital Atherectomy System for atherosclerotic plaque removal in *de novo* target lesions in the peripheral vasculature of the lower extremities.

## 4 STUDY DESIGN

#### 4.1 Overview

This is a first in human (FIH) prospective, two-center, non-randomized single-arm study designed to evaluate the safety and effectiveness of the FreedomFlowTM Orbital Atherectomy System in subjects diagnosed with peripheral arterial disease of the lower extremities.

# 4.2 Sample Size and Number of Centers

The study may enroll up to 10 subjects and will be conducted at up to 2 investigational sites in the United States.

# 4.3 Study Duration

Enrollment is expected to take approximately 2 months with observation periods at time of procedure, pre-discharge, 30 days, and 6 months post-procedure follow-up.

#### 5 STUDY ENDPOINTS

# 5.1 Primary Safety Endpoints

The primary safety endpoint is freedom from a composite of new on-set major adverse events (MAE) through 30-day follow-up as adjudicated by an independent clinical adjudicator.

The components of the MAE are defined as:

- Cardiovascular related death: All cardiovascular cause mortality.
- **Myocardial infarction (MI):** Any newly diagnosed MI post procedure, defined as CK-MB ≥2X upper limit normal (ULN).
- Clinically driven target lesion revascularization (TLR): any repeat percutaneous or surgical intervention to treat objectively documented symptoms of recurrent ischemia attributable to the treated lesion.
- Clinically significant target vessel dissection: NHLBI grade C or greater as confirmed by angiography.
- Clinically significant target vessel perforation: NHLBI Type III as confirmed by angiography.
- **Unplanned major target limb amputation:** Amputation of the transmetatarsals or higher that was not previously planned as part of the overall treatment strategy.
- Clinically relevant distal embolization: Emboli requiring surgical or medical intervention and/or the presence of symptoms.
- **Pseudoaneurysm:** disruption of the arterial wall at the treatment site as confirmed by angiography.

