#### 7.2 Risks

The risks of the investigational procedure to subjects is similar to that of other Atherectomy procedures.

Possible risks associated with the Cardio Flow FreedomFlowTM Orbital Atherectomy System that may occur and/or require intervention include, but are not limited to:

- Allergic reaction to medication/media/device components
- Amputation
- Anemia
- Aneurysm
- Bleeding complications which may require transfusion
- Cerebrovascular accident (CVA)
- Death
- Distal embolization
- Device embolization
- Entry site complications including hematoma
- Hemolysis
- Hypotension/hypertension
- Infection
- Myocardial infarction
- Pain
- Pseudoaneurysm
- Restenosis of treated segment that may require revascularization
- Renal insufficiency/failure
- Slow flow or no reflow phenomenon
- Dissection
- Perforation
- Thrombus

- Vessel closure, abrupt
- Vessel injury, including dissection and perforation that may require surgical repair
- Vessel spasm
- Vessel occlusion

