#### 8 STATISTICS

This study is a one or two center, prospective, non-randomized single-arm Early Feasibility Study. All clinical endpoints will be summarized with descriptive statistics without hypothesis testing. For continuous variables, the range (minimum, maximum), mean, standard deviation, median, first and third quartiles (Q1 and Q3) may be reported, while for discrete variables, count and percentage will be provided.

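### Cardiovascular death is the only kind of death in the MAE composite, so a subject who dies of another cause by day 30, with no other component, scores as free from MAE.

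*Combined protocol and SAP*

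**What the plan says.** Section 5.1 defines the primary safety endpoint as "freedom from a composite of new on-set major adverse events (MAE) through 30-day follow-up as adjudicated by an independent clinical adjudicator". Eight components follow, and the synopsis gives the same list. The one fatal component is cardiovascular death, explained only as "All cardiovascular cause mortality". The other seven are myocardial infarction, clinically driven target lesion revascularization, dissection, perforation, unplanned major amputation, distal embolization and pseudoaneurysm.

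Other provisions that bear on the point:

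- **Population.** Synopsis, Analysis Population: "The primary analysis will be based on the intent-to-treat (ITT) population".
- **Size.** Section 4.2: "The study may enroll up to 10 subjects".
- **Analysis.** Section 8: "All clinical endpoints will be summarized with descriptive statistics without hypothesis testing".
- **Procedure Success (Section 5.3.2).** It requires no MAE related to the procedure, residual stenosis of at most 50%, and no malfunction that aborts the procedure.
- **Secondary safety (Section 5.3.1).** Serious adverse events related to the device or procedure are an endpoint at 30 days and 6 months. Under Section 11.1 an event that led to death is serious.
- **Death reporting (Section 11.7, Table 12-1).** Every death goes to the sponsor, in writing within 48 hours.
- **Adjudication (Section 12.2).** One independent physician decides whether an event contributes to the endpoint and whether the subject is a procedural success.

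**The concern.** A freedom-from endpoint scores as favourable every subject who has no listed event. If a kind of death is not listed, the worst outcome can be scored as a success. Section 7.2 itself foresees routes to death that need not be cardiovascular: infection, renal failure, allergic reaction, and "Bleeding complications which may require transfusion".

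Two things are at stake. In a first-in-human study with descriptive analysis only, the primary rate is the main safety summary, and it could read 100% although a subject died of the procedure. The score also turns on a cause-of-death judgement for which the plan gives no definition and no default when the cause is unclear. Section 11.7 accepts that a death certificate or autopsy report may not exist.

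**Working it through.** The plan states no power, error rate or target for this endpoint, so there is no figure to reproduce. The check traces the definitions and then sizes the effect.

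**Step 1: how one death is scored.** Take a subject who is treated, dies of sepsis on day 20, and has none of the seven non-fatal components.

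| Rule | Result |
|---|---|
| Fatal component (synopsis, 5.1) | Not met if the death is judged non-cardiovascular |
| Other seven components | Not met, by assumption |
| Analysis population (synopsis) | Stays in the denominator under intent-to-treat |
| Competing-event, missing-data or unknown-cause rule | None given |
| Primary endpoint | Free from MAE |
| Procedure Success, MAE criterion (5.3.2) | Met, even if the sepsis was procedure-related |

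**Step 2: effect on the rate.** Assume 10 subjects, one such death and no other event. The exact 95% (Clopper-Pearson) limits are for illustration. Section 8 plans only counts and percentages for discrete variables.

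| Scoring | Rate | Exact 95% interval |
|---|---|---|
| As written | 10/10 = 100% | 69.2% to 100% |
| Death from any cause counts | 9/10 = 90% | 55.5% to 99.7% |
| Subject dropped as not evaluable (a rule the plan does not give) | 9/9 = 100% | 66.4% to 100% |

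The first lower limit is 0.025^(1/10) = 0.692.

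**Step 3: how likely is such a death?** The documents give no 30-day rate of non-cardiovascular death after this procedure. Over an assumed risk p per subject, the chance of at least one in 10 is 1 − (1 − p)^10:

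| Assumed p | Chance of at least one |
|---|---|
| 0.5% | 4.9% |
| 1% | 9.6% |
| 2% | 18.3% |
| 3% | 26.3% |
| 5% | 40.1% |

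These values of p are assumptions, and nothing in the documents supports one over another.

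**Step 4: the price of counting all deaths.** An unrelated background death would now count as a failure. Section 1 gives mortality of about 30% at five years and says "Overall, CVD causes death in 75% of PAD patients", which leaves 25% for other causes. With a constant hazard:

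- Hazard = −ln(0.70)/5 = 0.0713 per year.
- Over 30 days = 0.0713 × 30/365 = 0.00586 per subject.
- Non-cardiovascular, 10 subjects = 0.00586 × 0.25 × 10 = 0.0147, about 1.5%.

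Section 1 also gives 50% at ten years and 75% at fifteen. These imply hazards of −ln(0.50)/10 = 0.0693 and −ln(0.25)/15 = 0.0924. The same steps give 1.4% and 1.9%, so the answer depends little on which figure is used.

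**The case against.** The strongest reply is that this is a choice of endpoint and not an error. The synopsis and Section 5.1 agree with each other, and a cause-specific component keeps unrelated deaths from counting against the device. A death from a procedural complication is still an endpoint event, because it is a serious adverse event under Section 11.1 and enters the secondary endpoint in Section 5.3.1. With at most 10 subjects, any death would be seen individually. There is no test, performance goal or stopping threshold for the rate to move.

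Most of this stands, and it rules out four stronger readings that a reader might infer:

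- **That non-cardiovascular deaths go unseen.** They do not. All are reported to the sponsor, and the related ones enter a secondary endpoint.
- **That every non-cardiovascular death scores as a success.** A subject who also had, for example, a Type III perforation or a pseudoaneurysm fails whatever the death is called. Since cardiovascular death is undefined, the adjudicator might also classify a fatal bleed as cardiovascular.
- **That the trial's conclusion or error rates change.** Section 8 rules out hypothesis testing, so none do.
- **That 1.5% is the chance of the harm.** It is the background rate, and so the cost of the fix. The documents do not allow the procedural rate to be estimated.

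The reply still leaves the primary percentage uncorrected. The secondary endpoint is also only a partial safety net, because it depends on a judgement of relatedness. Section 11.5.3 grades relationship to the device only and has no scale for the procedure. A death judged non-cardiovascular and unrelated enters no safety endpoint, and all-cause 30-day mortality is not an endpoint anywhere.

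**Conclusion.** The point holds at modest severity. By definition, one non-cardiovascular death by day 30 without another component leaves the descriptive primary rate at 10/10 instead of 9/10, and the same subject can meet Procedure Success. The effect is confined to those two results.

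The conclusion rests on three assumptions: intent-to-treat keeps the subject in the denominator, all 10 subjects are enrolled, and no other event occurs. The plan never says in words that such a subject counts as event-free. That follows from the component list, the analysis population and the absence of any other rule. Section 12.2 lets the adjudicator decide what contributes to the endpoint and who is a procedural success, but gives no criterion that would bring such a death in.

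**What to change.** In the synopsis and Section 5.1, replace the fatal component with: *Death from any cause through 30-day follow-up.* Beside the composite, list each death with its adjudicated cause and its relationship to the device and to the procedure, so that unrelated deaths can be identified. Procedure Success keeps its restriction to procedure-related MAE, so an unrelated death would not count against it.

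The cost is an amendment to endpoint wording. No visits or subjects are added, and all deaths are already reported and adjudicated. Relationship to the procedure has to be recorded for each death, which Section 11 does not now define, although the secondary endpoint already needs it. The downside is the background death sized above, roughly a 1.5% chance across 10 subjects.

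If the sponsor prefers to keep a cause-specific component, the minimum is to define cardiovascular death, state how a death of unknown cause is scored, and report all-cause 30-day mortality beside the composite.

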# 6.4 Baseline Evaluation (Within 30 Days of Index Procedure)

Subjects that meet the pre-screening eligibility criteria and signed informed consent will have the following collected. These evaluations can occur anytime within 30 days of the procedure to the day of treatment. Only one angiogram is required.

- Demographic Information: race, age, weight, height
- Medical History / Current Status
- Physical Exam and Vital Signs
- Angiogram (recorded and sent to sponsor)
- Duplex Ultrasound (if available, recorded and sent to sponsor)
- Rutherford Classification
- Laboratory Assessments:
  - o CBC, creatinine, and potassium (on day of procedure)
  - o INR & PT if subject is on chronic warfarin therapy (on day of procedure)
  - Urine pregnancy test if female of child-bearing potential (within 7 days of procedure)
  - Hemoglobin, hematocrit, and free hemoglobin (pre-procedure, immediately post-procedure, and at discharge).

- VascuQoL Questionnaire
- Ankle Brachial Index (ABI)
- Concomitant Medications

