# 6.6 Post Procedure to Discharge

The following assessments will be performed within 12-24 hours post procedure or prior to hospital discharge, whichever occurs first:

- Physical Exam and Vital Signs
- Hemoglobin, hematocrit, and free hemoglobin
- Adverse Events assessment

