# 6.7 30 Days Follow-up (± 7 Days)

Subjects will return for a follow-up visit at 30 days and the following assessments will be performed:

- Physical Exam and Vital Signs
- Rutherford Classification
- ABI
- Duplex Ultrasound of treated lesion per Ultra Sound Core Lab protocol
- Angiogram performed only if clinical symptoms requiring intervention during follow-up for TVR or TLR
- VascuQoL Questionnaire
- Adverse Events assessment

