**Table 6-1: Schedule of Events** 

Assessment	Screening / Baseline/Pre- procedure	Procedure	Discharge	30 Days (±7 days)	6 months (±14 days)
Informed Consent	X				
Medical History	X				
Physical Exam	X		X	X	X
Laboratory Assessments	X	X			

Urine Pregnancy Test if female	X				
Rutherford Classification	X			X	X
ABI	X			X	X
VascuQoL Questionnaire	X			X	X
Hemoglobin, hematocrit, and free hemoglobin	X	X	X		
Angiogram	X	X		X a	X a
Duplex Ultrasound	X b			X	X
Medications	X		X	X	X
Adverse Events	X	X	X	X	X

<sup>aAngiograms will be performed at the follow-up visits for verification of restenosis of the treated lesion/vessel site(s) only if the subject has clinical symptoms requiring intervention.

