# 6.9 Unplanned Follow-up

Subjects returning for unscheduled visits complaining of new signs and/or symptoms will be documented as an unplanned follow-up and, at the investigators' discretion perform diagnostic evaluations. The reason should be reported as an adverse event if applicable.

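### MI in the primary safety endpoint is defined only by CK-MB, a test that no visit schedules, so the MAE count can miss silent MIs and MIs shown by another marker

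*Combined protocol and SAP*

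**What the plan says.** Section 5.1 and the synopsis define the MI component of the 30-day MAE composite in the same way: "Any newly diagnosed MI post procedure, defined as CK-MB ≥2X upper limit normal (ULN". Neither offers an alternative based on another marker, an ECG, imaging or a clinical diagnosis.

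The assessments are listed as follows.

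- Section 6.4 itemises the laboratory work: "CBC, creatinine, and potassium (on day of procedure"; INR and PT for subjects on warfarin; a pregnancy test where relevant; and "Hemoglobin, hematocrit, and free hemoglobin (pre-procedure, immediately post-procedure, and at discharge".
- Section 6.6 repeats only the three hemoglobin measures, taken "within 12-24 hours post procedure or prior to hospital discharge, whichever occurs first".
- Sections 6.7 and 6.8 (30 days and 6 months) list no laboratory test.
- Table 6-1 has a general laboratory row, marked at baseline and procedure but not at discharge or 30 days. It does not name CK-MB.
- Section 6.9 lets sites, at an unscheduled visit for new symptoms, "at the investigators' discretion perform diagnostic evaluations".

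Section 5.3.2 makes the absence of a procedure-related MAE one condition of Procedure Success. Section 8 plans descriptive summaries only. It does not say how a component is scored when the measurement that defines it was not taken.

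**The concern.** One component of the primary safety endpoint depends on a test that the protocol does not ask anyone to do. Whether an MI enters the MAE count may then depend on local ordering habits at one or two sites, and not only on whether the MI happened.

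MI is a real possibility here. Section 7.2 lists it among the device risks, and the background section says: "About 90% of patients with symptomatic PAD have coronary artery disease (CAD) as well". The study is first-in-human and tests no hypothesis, so no alpha or power is affected. What is at stake is whether the reported MAE-free rate, and the Procedure Success rate that draws on it, mean what they appear to mean in the 30-day and final reports.

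**Working it through.** The plan states no figure to reproduce. The check sets the definition beside the schedule, then gives a sense of scale.

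**Step 1: is CK-MB scheduled anywhere?** The definition needs a CK-MB value and an upper limit of normal. Sections 6.4, 6.6, 6.7 and 6.8 do not list CK-MB. The only itemisation of the general laboratory row in Table 6-1 is the one in Section 6.4, which omits it. No list contains troponin or an ECG either. Outside the MI definition, the documents do not mention CK-MB.

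**Step 2: what happens to each kind of MI if the text is followed?**

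| Case | How it comes to light | Meets the written MAE definition? |
|---|---|---|
| Fatal MI | Death report | Yes, as cardiovascular death |
| Symptomatic MI, site measures CK-MB at or above 2x ULN | Clinical work-up | Yes |
| Non-fatal MI within 30 days, shown by another marker, no CK-MB | Clinical work-up, AE or SAE report | No, read literally |
| Silent MI around the procedure | Only if the site orders CK-MB unprompted | Only if CK-MB happens to be measured |
| Isolated CK-MB rise at or above 2x ULN, no clinical MI diagnosis | Only if CK-MB is measured | Arguably yes; the text does not settle it |

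The third and fourth rows are the gap. The fifth is a second ambiguity, and it becomes more important once CK-MB is scheduled.

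**Step 3: direction.** If a component without a measurement is scored as not having occurred, a missed MI can only raise the MAE-free rate. The same holds for Procedure Success when the MI is procedure-related.

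**Step 4: scale.** Section 4.2 allows up to 10 subjects. If one subject has an uncounted MI and no other MAE, the result moves from 9/10 = 90% (exact 95% interval 55.5% to 99.7%) to 10/10 = 100% (69.2% to 100%). That is 1/10 = 10 percentage points. It shows what one subject weighs; it does not estimate bias.

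**Step 5: illustration with assumed rates.** The documents give no MI rate. Let p be the assumed chance per subject of an MI missed for these reasons. The chance of at least one in 10 subjects is 1 − (1 − p)^10:

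- p = 1%: 1 − 0.99^10 = 9.6%
- p = 2%: 1 − 0.98^10 = 18.3%
- p = 5%: 1 − 0.95^10 = 40.1%

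The expected overstatement of the MAE-free rate is at most p, and less if the same subject has another MAE.

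**The case against.** The best reply is that few such events would really be lost. Section 6.5 has the procedure done under site standard practice, which may include CK-MB, and Section 6.9 permits work-up of new symptoms. A symptomatic MI would probably qualify as an SAE under Section 11.1. Section 11 filters abnormal laboratory values only when they are non-cardiovascular, so an abnormal cardiac marker, once measured, should be recorded. Under Section 12.2 the adjudicator sees all available data and rules on whether an event contributes to the endpoint. The definition can also be read as event-triggered: an MI is diagnosed first and CK-MB confirms it, with no promise to screen everyone.

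Much of this stands. A reader might infer that silent MIs, or those shown by another marker, would disappear from the study. The documents do not support that: a site may obtain a CK-MB, and a diagnosed MI stays in the safety data whatever its MAE label.

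Two things survive. First, the adjudicator has no written criterion other than CK-MB. Counting an MI without it departs from the definition, and not counting it understates the MAEs. The event-triggered reading does not remove this. Second, detection of a silent MI is left to local habit. The event-triggered reading makes that a defensible choice only if the protocol says so, and it does not.

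**Conclusion.** The point holds as a mismatch between an endpoint definition and the schedule meant to support it. Followed literally, the plan can give a wrong MAE count, and it should be corrected. This rests on the text and needs no assumption about event rates. The direction of error assumes that an unmeasured component is scored as absent, which the protocol neither states nor rules out.

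The number of affected subjects cannot be estimated from the documents. The rates in the working are assumptions, and 10 points is only the weight of one subject in 10.

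A reader might also take the background figure on coronary disease to mean that about 9 of 10 subjects carry a material MI risk. The documents do not support that step. The figure describes symptomatic patients in general, Section 6.1.2 excludes unstable coronary disease and MI within 2 months, and prevalence of coronary disease is not a 30-day MI risk.

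This is a flaw in one component of a small descriptive study, and no test or success threshold depends on it.

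**What to change.** Reconcile the definition with the schedule.

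1. **Measure it.** Add CK-MB to the pre-procedure, immediate post-procedure and discharge hemoglobin draws in Sections 6.4 and 6.6 and in Table 6-1. The first draw gives a baseline against which a rise can be called new. Report how many subjects were measured at each draw.
2. **Widen the definition.** In Section 5.1 and the synopsis, let an adjudicated MI through day 30 also count when documented by another cardiac biomarker, against a criterion fixed in writing before enrollment.
3. **Settle isolated rises.** State in advance whether a CK-MB rise to at least 2x ULN without a clinical MI diagnosis is an MAE. The present wording arguably makes it one. Report the MAE-free rate with and without such rises.

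Cost: at most 3 draws × 10 subjects = 30 assays, with no extra visit or needle stick because the draws already exist. The rest is wording.

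Downside: the MAE-free rate may come out lower. The discharge draw may also be early, since Section 6.6 ties it to whichever comes first, so a late rise or a silent MI after discharge could still be missed. State this as a limitation in the report.
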